7.5 SECONDARY ENDPOINT(S)

7.5.1 Key secondary endpoint(s)

Not applicable.

7.5.2 (Other) Secondary endpoint(s)

Refer to [Section 7.8.5](#) for the analyses of secondary endpoints.

7.7 EXTENT OF EXPOSURE

A descriptive statistics table with mean, SD, median and range of the number of days a patient was on treatment will be provided for the TS. The tables will also provide the sum total of the time (in years) that all patients pooled together were on treatment. A separate listing will be created of any patients that switched treatment at any time indicating exposure to each treatment. A frequency table of number and percent of patients belonging to each categorical range of exposure weeks will be provided as well. The following are the categories of exposure-ranges (in weeks):

0 to <4, 4 to <12, 12 to <24, 24 to <36, 36 to <51 and >=51.

7.8 SAFETY ANALYSIS

All safety analyses will be performed on the TS.

7.8.1 Adverse Events

AEs will be coded using the latest version of the MedDRA coding dictionary at DBL. The analyses of AEs will be descriptive in nature. All analyses of AEs will be based on the number of patients with AEs (NOT the number of AEs). For analysis of multiple AE occurrences, data from the eCRF will be collapsed into an AE provided that all of the following applies:

- All AE attributes are identical (including LLT, intensity, action taken, therapy required, seriousness, reason for seriousness, relationship, outcome, AE of special interest and also additional information of specific AEs or AESIs).
- The occurrences were time-overlapping or time-adjacent (time-adjacency of 2 occurrences is given if the second occurrence started on the same day or on the day after the end of the first occurrence).

For further details on summarization of AE data, please refer to the guideline “Analysis and Presentation of Adverse Event Data from Clinical Trials” ([7](#)).

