5.2.6.2 Adverse event collection and reporting

5.2.6.2.1 AE Collection

The investigator shall maintain and keep detailed records of all AEs in the patient files.

The following must be collected and documented on the appropriate eCRF(s) by the investigator:

- From signing the informed consent onwards until the individual patient's end of study (EOS):
all AEs (serious and non-serious) and all AESIs.
- After the individual patient's end of trial:
the investigator does not need to actively monitor the patient for new AEs but should only report any occurrence of cancer and trial treatment related SAEs and trial treatment related AESIs of which the investigator may become aware of by any means of communication, e.g., phone call. Those AEs should be reported on the BI SAE form (see Section 5.2.6.2.2), but not on the eCRF.

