7.1 NULL AND ALTERNATIVE HYPOTHESES

The effect of empagliflozin 10 mg will be tested against placebo at a two-sided $\alpha = 0.05$ level of significance.

H0: Mean change from baseline in HbA1c after 52 weeks of treatment with empagliflozin 10 mg = mean change from baseline in HbA1c after 52 weeks of treatment with placebo

against

H1: Mean change from baseline in HbA1c after 52 weeks of treatment with empagliflozin 10 mg \neq mean change from baseline in HbA1c after 52 weeks of treatment with placebo.

The primary endpoint will use HbA1c units of %.

Secondary endpoints and further endpoints will be evaluated in an exploratory manner.

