7.5 DETERMINATION OF SAMPLE SIZE

Based upon previous experiences with these compounds, the difference in HbA1c change from baseline after 52 weeks between the treatment groups can be assumed to be 0.5% with a standard deviation of 0.85%. With a randomisation ratio of 1:1, it is assumed that the sample size of each group (empagliflozin 10 mg and placebo) is 62 patients. Assuming that approximately 3% of patients will not be eligible for inclusion into FAS due to the absence of a post-baseline primary endpoint value, 64 patients for the empagliflozin 10 mg group and 64 patients for the placebo group need to be randomised. With this sample size, a power of 90% for a two-sided test at level $\alpha=5\%$ for the primary endpoint will be achieved.

Calculations were performed using nQuery Advisor® 6.1 statistical package by [REDACTED]
[REDACTED].

8. INFORMED CONSENT, TRIAL RECORDS, DATA PROTECTION, PUBLICATION POLICY, AND ADMINISTRATIVE STRUCTURE

The trial will be carried out in compliance with the protocol, the ethical principles laid down in the Declaration of Helsinki, in accordance with the ICH Harmonised Guideline for GCP, relevant BI Standard Operating Procedures (SOPs), the Japanese GCP regulations (Ministry of Health and Welfare Ordinance No. 28, March 27, 1997), Good Post-Marketing Study Practice (GPSP), Good Vigilance Practice (GVP) and other relevant regulations. Investigators and site staff must adhere to these principles. Deviation from the protocol, the principles of ICH GCP or applicable regulations will be treated as “protocol deviation”.

Standard medical care (prophylactic, diagnostic and therapeutic procedures) remains the responsibility of the treating physician of the patient.

The investigator will inform the sponsor immediately of any urgent safety measures taken to protect the trial patients against any immediate hazard, as well as of any serious breaches of the protocol, of ICH GCP, or of Japanese GCP.

The Boehringer Ingelheim transparency and publication policy can be found on the following web page: trials.boehringer-ingelheim.com. The rights of the investigator and of the sponsor with regard to publication of the results of this trial are described in the investigator contract. As a rule, no trial results should be published prior to finalisation of the clinical trial report.

The certificate of insurance cover is made available to the investigator and the patients, and is stored in the ISF.

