7.8.1.1 Assignment of AEs to treatment

The analysis of adverse events will be based on the concept of treatment emergent adverse events. This means that all adverse events occurring between first drug intake until 7 days after last drug intake will be assigned to the first treatment received. All adverse events occurring before first drug intake will be assigned to 'pre-treatment' and all adverse events occurring after last drug intake + 7 days will be assigned to 'post-treatment'.

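### The general AE, SAE and AESI tables give crude patient percentages with no adjustment for time at risk, and no visible table compares by arm the serious events that start more than 7 days after stopping

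*SAP*

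**What the plan says.** SAP 7.8.1 sets the counting unit: "All analyses of AEs will be based on the number of patients with AEs (NOT the number of AEs"). SAP 7.8.1.2 then plans frequencies of patients by treatment, system organ class and preferred term, with separate tables for AESIs, serious AEs, AEs leading to discontinuation, AEs leading to death and drug-related AEs. The opening of SAP 7 takes percentages over all patients in the relevant set, and SAP 7.8 makes that the treated set.

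SAP 7.8.1.1 assigns to treatment the events from first dose to 7 days after last dose. Beyond that, "all adverse events occurring after last drug intake + 7 days will be assigned to 'post-treatment". Protocol 7.2.5 uses the same window, which is the residual effect period in Protocol 1.2.

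Collection runs longer than the window. Under Protocol 5.2.6.2.1 all AEs and AESIs are recorded "From signing the informed consent onwards until the individual patient's end of study (EOS"), and Protocol 3.3.4.1 has patients who stop early followed to the end of the trial.

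SAP 7.7 tabulates days on treatment, exposure categories and the "sum total of the time (in years) that all patients pooled together were on treatment", but does not link exposure to AE counts. SAP 7.8.1.3 treats hypoglycaemia more fully, with a descriptive event rate, Kaplan-Meier time to first event and a logistic model. SAP 7.8.1 refers further AE summary detail to an internal guideline that is not among the documents.

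**The concern.** A percentage of all treated patients compares the arms fairly only if they are at risk for about the same time. A patient who stops at Week 6 without an event counts the same as one observed event-free for 52 weeks. With equal hazards, the arm that stops earlier shows fewer patients with events.

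The documents give reasons why stopping might differ. Table 1.4.2:1 of the protocol expects more treatment failure on placebo, and Protocol 3.3.4.1 ends trial treatment for lack of efficacy when rescue does not suffice. The same section also lists hypoglycaemia and medically significant events, which could act the other way. The net direction is therefore unknown.

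A second gap follows from the window. A serious event that starts more than 7 days after stopping is recorded, but no visible table sets such events side by side by arm.

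**Working it through.** **1. What the plan quantifies.** No AE rate and no treatment-stopping rate is stated. The only calculation is for HbA1c (Protocol 7.5). It takes a difference that "can be assumed to be 0.5% with a standard deviation of 0.85"%. A two-sided 5% t test with 62 per arm has 90.1% power (89.7% with 61), and 62 / 0.97 = 63.9, so 64 per arm. The plan's figures reproduce, but only the arm size of 64 is used here. The 3% in that section is exclusion from the full analysis set and cannot serve as a stopping rate.

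**2. Assumptions.** True 52-week risk 20% in both arms; constant hazard; a proportion d of the arm stops, uniformly over 52 weeks and unrelated to AEs; window to last dose + 7 days.

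**3. Formula**, with time in units of 52 weeks, h = −ln(0.80) = 0.2231 and c = 7/364:

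- Completer: 1 − exp(−h(1 + c)) = 20.34%
- Stopper, averaged over stopping times: 1 − exp(−hc)(1 − exp(−h))/h = 10.76%
- Arm percentage: (1 − d) × 20.34% + d × 10.76%

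**4. Results**

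| Stopping, empagliflozin / placebo | Expected % with event | Ratio | Patients per 64 |
|---|---|---|---|
| equal | equal | 1.00 | 0 |
| 5% / 20% | 19.9 / 18.4 | 1.08 | 0.9 |
| 10% / 30% | 19.4 / 17.5 | 1.11 | 1.2 |
| 15% / 5% | 18.9 / 19.9 | 0.95 | −0.6 |

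**5. Against chance.** The 95% half-width for a difference at 20% with 64 per arm is 1.96 × √(2 × 0.2 × 0.8 / 64) = 13.9 points. The differences above are 1.4, 1.9 and −1.0 points.

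**6. Another stopping pattern.** Take exponential stopping with λ = −ln(1 − p)/52 and μ = −ln(1 − d)/52. The arm percentage is then 1 − exp(−λ) × [μ/(μ + λ) × (1 − exp(−52(μ + λ))) + exp(−52(μ + λ))]. At p = 30%, stopping of 10% / 20% gives 29.1% / 27.6%, and 10% / 30% gives 29.1% / 26.0%: about 1 and 2 patients per 64, against a half-width of 15.9 points. For true risks from 5% to 70% the ratio is 1.05 to 1.06 for 10% / 20%, 1.10 to 1.12 for 10% / 30%, and 0.95 to 0.96 for 20% / 10%.

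**7. Person-time outside the window.** This is about d × (0.5 − c). At d = 20% it is 0.2 × 0.481 = 0.096, or 6.2 of 64 patient-years. It is an upper figure, because it takes every stopper to be followed to Week 52.

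**8. With time at risk in the denominator.** Under the same assumptions, first events per patient-year have an expected ratio of 1.00 whatever the stopping rates.

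**The case against.** The case on the other side is substantial.

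- **Hypoglycaemia.** A reader might infer that every AE analysis ignores time at risk. It does not: SAP 7.8.1.3 plans Kaplan-Meier time to first hypoglycaemia on confirmed events, and an event rate. The logistic model has no exposure term, but this event is largely covered. The objection stands.
- **Unequal stopping is not established.** Treatment failure leads first to rescue while trial drug continues (Protocol 4.2.1), and only failed rescue ends trial treatment. Protocol 3.2 expects a low risk of significant hyperglycaemia, and planned duration is 52 weeks in both arms. The 20% and 30% are assumptions. This stands, so the bias is conditional.
- **Tolerability.** A reader might take the 0.95 ratio to show that stopping for side effects makes empagliflozin look safer. The calculation assumes stopping unrelated to AEs. A patient who stops because of an AE is already counted in the any-AE and discontinuation tables, so the cut-off cannot remove that patient. The figure does not support that reading.
- **Follow-up after stopping.** A reader might infer that a comparison over equal follow-up is ready to hand. Flow chart note 2 and Protocol 6.2.2 make it depend on the patient's agreement; otherwise the end-of-study visit comes 7 days after the end-of-treatment visit, close to the existing cut-off.
- **The unseen guideline.** It may already require such tables, so saying that later serious events enter no arm comparison at all would go too far. Only their absence from the visible text can be stated.
- **The counting sentence proves little alone.** It contrasts patients with events, and a rate of patients with a first event would also satisfy it. The denominator rule in SAP 7 and the window in SAP 7.8.1.1 carry the point.
- **Impact.** The tables are descriptive with no testing, the 7-day window is deliberate, and disposition and exposure are reported. That keeps the point minor. It does not remove it: total time on treatment does not let a reader rebuild time to first event, or find serious events after the window.

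**Conclusion.** The point holds in a limited form. The general AE, SAE and AESI tables would be modestly biased if stopping differed between arms, towards fewer events in the arm that stops more. For a 20% true risk the size is a ratio of about 1.08 to 1.11 under assumed stopping of 5% against 20%, or 10% against 30%: roughly 1 patient per 64 and well inside chance variation. This rests on equal constant hazards, stopping unrelated to AEs, and rates that the documents do not supply. With equal stopping there is no such bias, so the documents do not support saying that the AE comparison is biased.

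The lack of a visible by-arm comparison of serious events after the 7-day window does not depend on those assumptions; it is subject only to what the internal guideline contains. Both are improvements to supplementary reporting and do not affect the primary analysis.

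**What to change.** Keep the planned n (%) tables. Add to SAP 7.8.1.2:

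1. For any AE, SAEs, AEs leading to discontinuation and AESIs, by arm: patients with a first event per 100 patient-years at risk, with time at risk running from first dose to the first event or last dose + 7 days, whichever is earlier. Give the rate difference and its 95% CI.
2. One supportive by-arm table of deaths, SAEs and AESIs from first dose to end of study, regardless of treatment status.

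If the internal AE guideline cited in SAP 7.8.1 already requires these, one sentence saying so is enough. In the same edit, exempt hypoglycaemia from the patients-only rule in SAP 7.8.1, since SAP 7.8.1.3 plans event totals and an event rate.

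The cost is SAP wording and a few tables from data already collected; trial conduct does not change. The downsides are small and should be footnoted. The rate assumes a roughly constant hazard. The to-end-of-study table dilutes on-drug effects, includes time on other antidiabetic therapy, and is incomplete for patients who decline follow-up.

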7.8.1.1 Assignment of AEs to treatment

The analysis of adverse events will be based on the concept of treatment emergent adverse events. This means that all adverse events occurring between first drug intake until 7 days after last drug intake will be assigned to the first treatment received. All adverse events occurring before first drug intake will be assigned to 'pre-treatment' and all adverse events occurring after last drug intake + 7 days will be assigned to 'post-treatment'.

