6. INVESTIGATIONAL PLAN

6.1 VISIT SCHEDULE

All trial visits except for screening (Visit 1) should take place in the morning. If a patient mistakenly takes trial medication in the morning of a visit before attending the clinic or comes in fed condition where a fasting condition is required, the visit should be rescheduled for another day as soon as possible reminding the patient of the expected conditions. The rescheduled visit must take place in a short enough time-frame so that the patient has sufficient trial medication available.

All patients are to adhere to the visit schedule as specified in the [flowchart](#). If any visit has to be rescheduled, subsequent visits should follow the original visit date schedule. The trial medication kits contain sufficient medication to allow for these time windows. The run-in period must be 14 to 21 days long prior to randomisation.

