7.2.5 Safety analyses

Adverse events will be coded using the Medical Dictionary for Drug Regulatory Activities (MedDRA). Standard BI summary tables and listings will be produced. All adverse events with an onset between start of double-blind treatment and end of the REP, a period of 7 days after the last dose of trial medication, will be assigned to the on-treatment period for evaluation.

All treated patients will be included in the safety analysis. In general, safety analyses will be descriptive in nature and will be based on BI standards. No hypothesis testing is planned.

Statistical analysis and reporting of adverse events will concentrate on treatment-emergent adverse events, i.e. all adverse events occurring between start of double-blind treatment and end of the REP. Adverse events that start before first double-blind drug intake and deteriorate under treatment will also be considered as 'treatment-emergent'.

Frequency, severity, and causal relationship of adverse events will be tabulated by system organ class and preferred term after coding according to the current version of the MedDRA at database lock. Adverse events of special interest (AESI) will also be summarised.

Laboratory data will be analysed both quantitatively as well as qualitatively. The latter will be done via comparison of laboratory data to their reference ranges. Values outside the reference range as well as values defined as clinically relevant will be summarised. Treatment groups will be compared descriptively with regard to distribution parameters as well as with regard to frequency and percentage of patients with abnormal values or clinically relevant abnormal values.

Vital signs, physical examinations, or other safety-relevant data observed at screening, baseline, during the course of the trial and at the end-of-trial evaluation will be assessed with regard to possible changes compared to findings before start of treatment.

Further details on the safety analysis will be specified in the TSAP.

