3. INTRODUCTION

As per ICH E9 ([1](#)), the purpose of this document is to provide a more technical and detailed elaboration of the principal features of the analysis described in the protocol, and to include detailed procedures for executing the statistical analysis of the primary and secondary variables and other data.

This TSAP assumes familiarity with the CTP, including Protocol Amendments. In particular, the TSAP is based on the planned analysis specification as written in the CTP Section 7 “Statistical Methods and Determination of Sample Size”. Therefore, TSAP readers may consult the CTP for more background information on the study, e.g., on study objectives, study design and population, treatments, definition of measurements and variables, planning of sample size, randomization.

SAS® Version 9.4 or a later version will be used for all analyses.

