4. CHANGES IN THE PLANNED ANALYSIS OF THE STUDY

Descriptions in the CTP related to statistical analysis will be changed as follows:

- [REDACTED]
- [REDACTED]
- [REDACTED]
- Descriptive statistics on the impact of COVID-19 on study visits as well as trial medication intake will be provided if any.
- The definition of iPDs will be specified in the DV domain instead of the TSAP prior to DBL.

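### The SAP defines treatment-emergent AEs by timing alone and omits the protocol's rule that events starting before double-blind dosing and worsening on treatment also count

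*SAP*

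**What the plan says.** Protocol 7.2.5 (Safety analyses) bases AE reporting on treatment-emergent events, which it defines as "all adverse events occurring between start of double-blind treatment and end of the REP". The residual effect period (REP) is 7 days after the last dose. The protocol then adds a second route into the category: "Adverse events that start before first double-blind drug intake and deteriorate under treatment will also be considered as 'treatment-emergent".

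SAP 7.8.1.1 (Assignment of AEs to treatment) also says that the AE analysis rests on the treatment-emergent concept. It spells this out as "all adverse events occurring between first drug intake until 7 days after last drug intake will be assigned to the first treatment received", and continues: "All adverse events occurring before first drug intake will be assigned to 'pre-treatment". Events after the 7-day period are post-treatment. The readable SAP says nothing about an event that begins before dosing and worsens afterwards.

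SAP section 3 states that "the TSAP is based on the planned analysis specification as written in the CTP Section 7", and the worsening rule sits in that section of the protocol. SAP section 4 opens its list of departures with "Descriptions in the CTP related to statistical analysis will be changed as follows". Two of its five bullets can be read (COVID-19 impact and where important protocol deviations are defined). The other three are redacted.

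**The concern.** The two documents place the same event in different categories. Suppose a patient develops a mild urinary infection in the placebo run-in and it becomes severe after randomised dosing starts. Under the protocol it is treatment-emergent. Under the literal SAP text it can be classed as pre-treatment, and so be absent from the tables by system organ class, intensity, seriousness, relatedness and discontinuation in SAP 7.8.1.2.

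At stake is how completely the AE tables describe deterioration on drug in an elderly population. The primary HbA1c analysis is not touched.

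**Working it through.** No sample-size, power or event figure in the plan bears on this point, so there is none to reproduce. The check sets the texts side by side and then sizes the exposed window.

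**1. On-treatment window.** Protocol: start of double-blind treatment to 7 days after the last dose. SAP: first intake to 7 days after the last intake. The windows agree, so the missing worsening rule is the substantive difference.

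**2. Are events with onset before dosing recorded at all?** Yes. Protocol 5.2.6.2.1 collects all AEs "From signing the informed consent onwards until the individual patient's end of study (EOS").

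**3. Length of the exposed window.**
- Run-in (Protocol 6.1): "The run-in period must be 14 to 21 days long prior to randomisation".
- Screening (Protocol 6.2.1): Visit 2 at most 7 days after Visit 1, extendable case by case.
- Shortest: 0 + 14 = 14 days. Longest without extension: 7 + 21 = 28 days.

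For a patient who completes 52 weeks (364 days) plus the 7-day period, the window is 14/(14 + 364 + 7) = 3.6% to 28/(28 + 364 + 7) = 7.0% of the combined time. If AE onset were uniform over time (an assumption), that would be the share of onsets falling in the window. Only those still present at first dose that then worsen are exposed.

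**4. Does anything else in the documents close the gap?**
- Protocol 5.2.6.1.1 makes a worsening of the diabetes or of another pre-existing condition an AE in its own right. Such a worsening would normally carry an on-treatment onset and be counted. The same section treats abnormalities present before trial inclusion as baseline conditions, so an AE that first appears after consent is not clearly covered.
- Protocol 5.2.6.2.2 requires follow-up of each event to an outcome. Nothing readable tells sites to close a record and open another when an AE worsens.
- The SAP 7.8.1 collapsing rule merges occurrences only when all attributes, including intensity, are identical. It therefore keeps a separately entered worsening separate, but it does not split a single record.

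The exposed case is thus an AE with onset between consent and first randomised dose, held as one record, that worsens on treatment.

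**5. Size per patient.** With 64 per arm, all treated: 1/64 = 0.0156, or about 1.6 percentage points of that arm's incidence. This is the step for one patient, not an estimate of how many there will be.

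**6. A related wording gap.** SAP 7.8.1.1 refers to first drug intake without saying which drug. A placebo run-in comes first, and Protocol 4.1.4 calls those tablets trial medication too. Protocol 7.2.5 names the double-blind drug, and SAP 6.7 names randomised trial medication when it defines baseline. SAP 7.8.1.1 should be equally specific.

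**The case against.** The SAP sentence concerns AEs occurring before first intake, not AEs that start before it. An event that straddles the first dose also occurs after it, and the preceding SAP sentence could capture it. The SAP presents itself as an elaboration of protocol section 7, so the worsening rule may still apply unrepeated. SAP 7.8.1 also defers to a sponsor AE guideline that may contain such a rule. Where sites enter a worsening as a new record, it is counted. AE analyses are descriptive, with no hypothesis tests, and the same rule applies to both arms. The special-interest categories are poor examples: hepatic injury and decreased renal function are laboratory thresholds, and liver-enzyme elevations and creatinine doubling are tabulated from laboratory data whatever the AE onset.

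Most of this stands and narrows the point. It does not remove it: one document states a rule, the other defines the same concept without it, and no readable text reconciles them.

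A reader might infer three stronger conclusions that the documents do not support:
- **That the literal SAP rule is what will be programmed.** The guideline is unavailable and the SAP leans on the protocol, so the programmed rule is unknown.
- **That the sponsor changed the definition without declaring it.** A redacted bullet in SAP section 4 could cover it.
- **That these events are counted in neither arm.** The text supports only that they can be missing from the on-treatment tables, under one reading and one recording practice.

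**Conclusion.** The inconsistency is real and worth correcting, but narrow. It matters if three things hold: the SAP wording is applied literally, the worsening is kept in the original AE record, and neither the redacted bullets nor the sponsor guideline restores the protocol rule. None of these can be verified from the documents.

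The number of patients affected cannot be calculated and may be small or zero. In tables with few events, such as serious AEs or discontinuations, one patient's step would be visible. No direction of bias between the arms is established.

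**What to change.** In SAP 7.8.1.1:
- Carry over the protocol rule: an AE that starts before the first intake of randomised (double-blind) medication and deteriorates between that intake and 7 days after the last intake is counted as treatment-emergent, at the worsened intensity.
- Replace the reference to first drug intake with first intake of randomised trial medication.

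If the sponsor prefers a timing-only definition, declare and justify that departure from Protocol 7.2.5 in SAP section 4. If the sponsor guideline or a redacted bullet already settles the matter, a cross-reference in 7.8.1.1 would do.

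The cost is one derivation flag, and AE counts may rise slightly. There is a practical limit: where a worsening is not entered as a separate record, its date may not be available. The SAP should therefore say how worsening is identified, from a new record or from an updated intensity. The rule should stay with deterioration, as the protocol has it. Adding a change in seriousness, or requiring a date of worsening, would go beyond the protocol and beyond what the documents show is collected.
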